4.2.3. Premature Withdrawal and Missing Data

If any missing data are present in diary data for any reasons, no imputation will be applied to derive responder. No explicit missing data imputation will be performed for change from baseline since a mixed model for repeated measures (MMRM) will be applied to change from baseline analysis. For responder analyses, subjects with missing assessments will be considered non-responders. Missing items from the questionnaires will be handled according to the respective measure instructions as described in [Section 4.3.3](#).

In general, missing safety data will not be imputed and only observed values will be analyzed.

If the relationship of an AE record (“Relationship to Study Treatment” on AE eCRF) is missing this AE will be considered “Probably Related” to the study treatment. If the AE severity is missing every effort should be made to acquire the information from the investigator. “Severe” will be assigned to a missing intensity for reporting purposes.

The general imputation rules of partial missing date for both AE and concomitant medication are detailed below:

Dates with missing the day of the year will adhere to the following conventions:

- The missing day of onset date will be set to:
 - First day of the month that the event occurred, if the onset YYYY-MM is after the YYYY-MM of the study treatment
 - The day of the study treatment, if the onset YYYY-MM is the same as YYYY-MM of the study treatment

- The date of informed consent, if the onset YYYY-MM is before the YYYY-MM of the study treatment.
- The missing day of end date will be set to:
 - The last day of the month of the occurrence. If the subject died in the same month, then set the imputed date as the death date.

Dates with missing both the day and month of the year will adhere to the following conventions:

- Missing day and month of onset date will be set to:
 - January 1 of the year of the onset, if the onset YYYY is after the YYYY of the study treatment
 - The date of the study treatment, if the onset YYYY is the same as YYYY of the study treatment
 - The date of informed consent, if the onset YYYY is before YYYY of the study treatment
- The missing date of end date will be set to:
 - December 31 of the year of occurrence. If the subject died in the same year, then set the imputed date as the death date.

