4.3.2. Bladder Diary Data

Bladder Diary data are collected following the schedule of assessments in Section 1.3 of the protocol. Per protocol diaries will not be collected if subjects receive additional OAB treatment(s) at Week 24 or after. For summary and analysis purpose, any bladder diaries collected after the first additional OAB treatment will not be included in defining the subsequent endpoints based on the bladder diaries. All bladder diaries collected will be included in the listings.

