7.2. Adverse Events

Adverse events (AEs) will be coded using MedDRA version 22.1. or later.

All reported AEs (whether treatment emergent or not) will be included in by-subject AE listings. Sorting will be by treatment, subject, date of event, SOC, PT and then verbatim description.

An AE will be considered a treatment emergent adverse event (TEAE) if it begins or worsens in severity after initial exposure of the study treatment through 48 weeks after treatment administration or the date of the initiation of another OAB medication, investigational agent or surgical intervention, whichever occurs first. The determination of "48 weeks" will be based on the study day of the AE start date instead of the visit date of the Week 48 visit. The OAB medication will be determined based on the checkbox "Is this an additional OAB medication"

on the concomitant medication CRF. After data are collected and reviewed by the clinical team, a blinded list of investigational agents and surgical interventions will be provided to the programming team prior to database lock to determine which AEs should no longer be considered treatment emergent due to possible confounding effects. Partial AE start dates will be imputed as detailed in [Section 4.2.3](#).

Summary tables will be based on TEAEs. The incidence of TEAEs will be presented using counts and percentages of subjects with TEAEs and tabulated by SOC and PT. SOC will be sorted in descending frequency and PT within SOC will be sorted by descending frequency based on the incidence of all subjects treated with URO-902 included in the summary. If a subject has multiple occurrences (start and stop) of an event associated with a specific SOC or PT within a SOC, a subject will only be counted once in the incidence count for the SOC or PT within SOC respectively.

An overall summary table of AEs by treatment group will be presented detailing the number and percentage of subjects, and number of events for the following categories:

- At least one TEAE;
- At least one Treatment-Related TEAE;
- At least one Grade ≥ 3 TEAE (Mild = Grade 1, Moderate = Grade 2, Severe = Grade 3, Life-Threatening = Grade 4, Death = Grade 5)
- At least one Grade ≥ 3 Treatment-Related TEAE;
- At least one Serious TEAE;
- At least one Serious Treatment-Related TEAE;
- At least one TEAE leading to Discontinuation from Study;
- At least one TEAE of Special Interest;
- At least one Treatment-Related TEAE of Special Interest

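### The SAP's earliest-date rule for partial medication dates can put the additional-OAB-medication cut-off before that medication could have begun

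*SAP*

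**What the plan says.** SAP 4.2.3 has one set of partial-date rules for two kinds of record: "The general imputation rules of partial missing date for both AE and concomitant medication are detailed below". For a start date on or after treatment:

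- Day missing, later month than treatment: "First day of the month that the event occurred, if the onset YYYY-MM is after the YYYY-MM of the study treatment". In the treatment month itself, the treatment day is used.
- Day and month missing, same year as treatment: "The date of the study treatment, if the onset YYYY is the same as YYYY of the study treatment".
- Day and month missing, later year: "January 1 of the year of the onset, if the onset YYYY is after the YYYY of the study treatment".

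Two other sections use the start of additional OAB medication as a cut-off. SAP 7.2 closes the treatment-emergent period at 48 weeks "or the date of the initiation of another OAB medication, investigational agent or surgical intervention, whichever occurs first". It also says "The OAB medication will be determined based on the checkbox" on the concomitant medication form, so the start is a concomitant-medication date. SAP 4.3.2 says that "any bladder diaries collected after the first additional OAB treatment will not be included in defining the subsequent endpoints". SAP 4.2.3 and 4.3.2.5 count a missing visit as non-response in the responder analyses.

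Protocol 9.5.2 did not end the treatment-emergent period at OAB medication. SAP 9 records that the SAP added this and removed the safety (modified) population. Protocol 6.9.2 permits additional OAB treatment from Week 24, but SAP 5.4.1 applies the flag whenever the treatment was received. No section sets a lower limit on the imputed date.

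**The concern.** Choosing the earliest date is cautious for AE onset, because it keeps an event inside the treatment-emergent period. For a date that closes the period, the same choice works in reverse: the period ends too soon. The imputed start of OAB medication can fall before Week 24, when such treatment was not yet permitted, and even on the treatment day.

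Two things follow for the subject concerned. AEs between the imputed and the true start lose treatment-emergent status and leave the TEAE tables by preferred term, including the serious and special-interest tables. Diaries completed in the same interval are dropped, so those visits are missing for the MMRM and are non-response in the responder analyses, although the subject had taken no other treatment.

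**Working it through.** The plan gives no figure for this rule, so there is none to reproduce. The check applies the rule to dates.

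**Inputs**
- Study day = date − treatment date + 1 (SAP 4.3.4).
- Target days (SAP Table 2) follow 7 × week + 1: Week 12 = 85, Week 18 = 127, Week 24 = 169, Week 36 = 253, Week 48 = 337.
- Diaries cover 3 consecutive days in the 7 before the visit timepoint (Protocol 1.3).
- Shift = true study day − imputed study day.

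**Limits of the shift for a true start on Days 169 to 337**
- Day missing: at most 31 − 1 = 30 days.
- Day and month missing, treatment year: the imputed day is always 1, so the shift runs from 169 − 1 = 168 to 337 − 1 = 336 days, and every post-baseline diary is dropped.
- Day and month missing, later year: the imputed date is 1 January.

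**Worked dates**

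| Treated | True start | Recorded as | Imputed | Shift |
|---|---|---|---|---|
| 10 Jan 2022 | 28 Jun 2022 (Day 170) | Jun 2022 | 1 Jun 2022 (Day 143) | 170 − 143 = 27 |
| 1 Feb 2021 | 15 Nov 2021 (Day 288) | 2021 | 1 Feb 2021 (Day 1) | 288 − 1 = 287 |
| 1 Sep 2021 | 1 Jun 2022 (Day 274) | 2022 | 1 Jan 2022 (Day 123) | 274 − 123 = 151 |

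In the first row a Week 24 diary kept in the week before Day 169 falls after Day 143 and is dropped. In the second row, six valid diary visits are lost (Weeks 2, 6, 12, 18, 24 and 36). In the third, Weeks 24 and 36 are lost and Weeks 2 to 12 are kept. Week 18 depends on which days the diary covered.

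Loss of Week 12 can also depend on the diary days. For a subject treated on 15 October 2021 with a start recorded only as 2022, the imputed date is Day 79. A diary on Days 82 to 84 is dropped, but one finished by Day 79 is kept.

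**Enumeration.** The documents give no dates or rates. Assume every treatment date in one calendar year is equally likely, every true start from Day 169 to Day 337 is equally likely, and each diary covers the 3 days before its target day.

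| | Day missing | Day and month missing |
|---|---|---|
| Shift, range | 0–30 days | 0–336 days |
| Shift, median | 15 days | 174 days |
| Imputed before Week 24 | 9% | 77% |
| Imputed to Day 1 | 0% | 31% |
| Week 12 diary lost | 0% | 53% |
| Mean valid diary visits lost | 0.15 | 3.1 |

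These percentages are conditional on a partial date of that type. They are not expected rates in the trial. One further case matters for the more likely type: if the medication starts at the Week 24 visit (Day 169) and only the day is missing, the Week 24 diary is dropped for 87% of treatment dates (diary on Days 166–168) or 74% (Days 162–164).

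**The case against.** The strongest reply is that this will seldom happen. Protocol 6.9 requires dates of administration on the eCRF. Protocol 6.9.2 has the subject ask for treatment and the investigator judge it appropriate, so a site that knows only the year is unlikely. This stands, and it limits the point to a few subjects at most. It does not make the rule harmless. The drug is not supplied by the sponsor, treatment may start between visits, later contacts are by telephone, and the SAP itself plans for partial dates.

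A second reply is that nothing vanishes. A reader might infer that AEs are erased; the documents do not support that. Table 14.3.1.14 summarizes AEs after the cut-off in the overall-summary layout, which has rows for serious, Grade 3 or higher and special-interest events. Deaths, SAEs, all AEs and all diaries are listed. What is lost is the preferred-term detail in the TEAE tables and the diary data in the endpoints.

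Third, a pre-Week-24 date would show in Table 14.1.5.3 and could resemble prohibited-medication use, so a gross error might be noticed. That is a chance of detection, but the SAP gives no rule for correcting the date.

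Fourth, SAP 7.2 refers back to 4.2.3 only for AEs: "Partial AE start dates will be imputed as detailed in" that section. On that narrow reading the OAB medication date has no stated rule for this use. The plain reading of 4.2.3 covers all concomitant medication. Either way, the SAP needs text.

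**Conclusion.** The point holds as a defect in a stated rule with limited reach. Followed as written, SAP 4.2.3 can place the cut-off for TEAEs and diaries before additional OAB medication could have begun. The size depends on what is missing: up to 30 days when only the day is unknown, and up to 336 days when day and month are both unknown.

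Two stronger readings are not supported. One is that any partly known date costs months; that requires both day and month to be missing. The other is that the treatment comparison is biased in a known direction. The documents give neither the rate of additional treatment by arm nor the rate of partial dates, so no direction can be claimed. One affected subject is 1/26 = 3.8% of a dose group. In an exploratory study with descriptive analyses, that is worth preventing but is no threat to the study.

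The limits of the shift rest only on the calendar and the visit days. The percentages rest on the uniform-date assumptions above.

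**What to change.** Add to SAP 4.2.3 that the imputed start of a medication flagged as additional OAB treatment:

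- may not be earlier than the day after the last visit or contact at which no such treatment was recorded;
- may not be earlier than the Week 24 visit, unless the record shows that it was taken before then;
- may not be later than the visit at which it was first reported.

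Within those bounds, keep the existing earliest-date rule. Leave the rule for AE onset unchanged. Protocol 1.3 schedules a concomitant-medication review at every visit, so the bounds need no new data.

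Applied to the worked dates, with visits on their target days and the treatment first reported at the next contact:

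- First row: the imputed day becomes 170, and the shift falls from 27 days to 0.
- Second row: Day 254, and the shift falls from 287 to 288 − 254 = 34 days.
- Third row: Day 254, and the shift falls from 151 to 274 − 254 = 20 days.

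Between Week 24 and Week 36 the remaining shift is at most 253 − 170 = 83 days. From Week 36 to Week 48 it is at most 337 − 254 = 83 days.

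Imputing the latest possible date is a tempting alternative, but it could keep up to about 84 days (253 − 169) of post-treatment time as untreated, which is hard to defend for efficacy. Investigational agents and surgery can stay outside this change: SAP 7.2 takes them from a separate blinded list, and 4.2.3 does not cover procedure dates.

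The cost is one SAP sentence and one programming branch. A small amount of time after additional treatment may be kept as before it, if an earlier contact failed to record treatment already started.

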#### **8.5.1. Time Period and Frequency for Collecting Adverse Event and Serious Adverse Event Information**

All AEs and SAEs will be collected from the signing of the ICF through 30 days after the end of the study at the timepoints specified in the Schedule of Assessments ([Section 1.3](#)), and as observed or reported spontaneously by study subjects. Medical occurrences that begin before the start of study drug, but after obtaining informed consent will be recorded in the AE section of the eCRF.

**All SAEs (including serious adverse events of special interest [AESIs]) will be recorded and reported on the eCRF within 24 hours of the study site personnel's knowledge of the event.** Marking the event as "serious" will automatically send required notifications for Sponsor or designee review. The investigator will also submit any updated SAE data within 24 hours of receipt of the information.

Nonserious AESIs will be reported on the eCRF within **72 hours** of the site's knowledge of the information.

Investigators are not obligated to actively seek AE or SAE information after conclusion of the study participation. However, if the investigator learns of any SAE, including a death, at any time after a subject has been discharged from the study, and he/she considers the event to be reasonably related to the study drug or study participation, the investigator must promptly notify the Sponsor or designee.

The method of recording, evaluating, and assessing causality of AEs and SAEs and the procedures for completing and transmitting SAE reports are provided in [Section 10.3](#).

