5.4. Prior and Concomitant Medication

Prior and concomitant medications will be coded using the World Health Organization (WHO) Drug B3-Sept Format, 2019 version. These medications will be further classified as follows.

- Prior medication is defined as those medications that started prior to the study treatment.
- Concomitant medication is defined as those taken on or after the study treatment. If medications started prior to the study treatment and were ongoing after the study treatment, those medication will be considered as concomitant medication as well.

The number and percentage of subjects taking prior and concomitant medications will be summarized overall by Anatomical Therapeutical Chemical (ATC) Levels 2 and 4 for all subjects in the safety population. Prior and concomitant medications will be listed for all subjects in the safety population.

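### SAP 4.2.3 moves partial onset dates to the treatment date without checking the end date, so an AE known to have ended before dosing counts as treatment-emergent and a drug known to have stopped leaves the prior-medication table.

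*SAP*

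**What the plan says.** SAP 4.2.3 sets out one family of rules for two kinds of record: "The general imputation rules of partial missing date for both AE and concomitant medication are detailed below".

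- Onset day missing, same month as dosing: "The day of the study treatment, if the onset YYYY-MM is the same as YYYY-MM of the study treatment".
- Onset day and month missing, same year as dosing: "The date of the study treatment, if the onset YYYY is the same as YYYY of the study treatment".
- Onset day missing, month before dosing: "The date of informed consent, if the onset YYYY-MM is before the YYYY-MM of the study treatment".
- End day missing: "The last day of the month of the occurrence", or the date of death if the subject died in that month.

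SAP 7.2 calls an AE treatment-emergent if it "begins or worsens in severity after initial exposure of the study treatment", up to a stated cut-off, and sends partial AE start dates through section 4.2.3. Events from before dosing are in the AE data by design; Protocol 8.5.1 states: "Medical occurrences that begin before the start of study drug, but after obtaining informed consent will be recorded" in the AE section of the eCRF. For drugs, SAP 5.4 says "Prior medication is defined as those medications that started prior to the study treatment", and defines concomitant drugs as those taken on or after it. Protocol 8.1.5 collects OAB drugs used over the past three years.

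**The concern.** Setting an uncertain onset to the treatment date is a sensible cautious default when the record could have begun after dosing. It is not sensible when the recorded end date shows that it could not. No branch of the rule makes that distinction, and no other section of either document supplies it. The output is then a record that starts after it ends and is counted in the wrong period.

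At stake are the TEAE counts, the main safety output of a small study, and the completeness of the prior-medication table. SAP 4.2.3 also sets a missing relationship to probably related, so a mislabelled event with that field blank would be tabulated as a treatment-related TEAE.

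**Working it through.** The plan gives no figure for this point, so there is none to reproduce. The check is to apply the rule as written.

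**Two worked records** (illustrative dates; treatment on 20 May 2021)

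- AE: onset May 2021, day unknown; recorded end 12 May 2021. The onset month equals the treatment month, so the imputed onset is 20 May. That is 20 − 12 = 8 days after the event ended, and the event is flagged as a TEAE.
- Drug: start 2021, day and month unknown; recorded stop 15 April 2021. The onset year equals the treatment year, so the imputed start is 20 May 2021. The drug no longer started before treatment, so it is not prior. If it is classified by start date alone it becomes concomitant. If the stop date is also used it was not taken on or after treatment, and it falls in neither table.

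**How often the AE rule would misfire, given a missing onset day**

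Inputs: the screening and randomization period is at most 35 days (Protocol 1.3, note a). Assumptions: dosing is equally likely on each day of a 365-day year; consent is L days before dosing; and every AE that starts *a* days and ends *b* days before dosing, with 1 ≤ *b* ≤ *a* ≤ L, is equally likely.

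There are L(L+1)/2 such AEs. If dosing is on day *d* of the month, the onset shares the dosing month when *a* ≤ *d* − 1. With k = min(*d* − 1, L), that is k(k+1)/2 of them. The share mislabelled is the mean of k(k+1) / [L(L+1)] over the 365 dosing dates.

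- L = 14: in each month, days 1 to 14 contribute the sum of k(k+1)/210 for k = 0 to 13, which is 910/210 = 4.333. Each later day contributes 1. Over the year this is 12 × 4.333 + (365 − 168) = 52 + 197 = 249, and 249/365 = 68.2%.
- L = 35: k is always *d* − 1, and a month of n days contributes (n−1)n(n+1)/3, which is 9,920, 8,990 or 7,308 for 31, 30 or 28 days. The year gives 7 × 9,920 + 4 × 8,990 + 7,308 = 112,708, and 112,708 / (1,260 × 365) = 24.5%.

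| Consent-to-treatment interval (days) | Onset day missing | Onset day and month missing |
|---|---|---|
| 7 | 83.6% | 98.6% |
| 14 | 68.2% | 97.4% |
| 21 | 52.9% | 96.1% |
| 28 | 37.5% | 94.8% |
| 35 | 24.5% | 93.5% |

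**With an end-date check.** If a known end is before treatment, set onset to the earlier of the imputed onset and the end date. The share mislabelled is then 0% in every row. An AE with onset in May and no end date still goes to 20 May, so the cautious default survives.

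**Size of one record.** The planned active arms have 26 subjects each (SAP 1.2.1), so one mislabelled subject moves an incidence by 1/26 = 3.8 percentage points.

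**The case against.** The best defence is that the effect is small and leans the safe way. Safety summaries are descriptive, the study is exploratory with about 78 subjects, and the rule applies alike to every arm. AEs are reviewed at Visits 1, 2 and 3 within at most 35 days, so few onset days should be missing and a year-only AE onset is less plausible still. The AE listing shows start date, stop date and treatment-emergent status, so an impossible pair would probably be noticed. All of this bears on priority. It does not make the written rule right, and noticing the pair in a listing does not correct the table.

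One could also read the TEAE definition strictly, so that an onset on the treatment date is not after exposure. That would defeat the purpose of imputing to that date, and SAP 7.2 counts from on or after the study dose in its additional AE table.

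Some stronger inferences are tempting but not supported:

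- *Washed-out OAB drugs would appear as prohibited use and corrupt the deviation list.* Neither document derives deviations from imputed dates, and a drug with a known pre-dose stop was not taken on or after treatment. The secure consequence is its loss from the prior-medication table.
- *The affected events are typically UTIs of special interest.* A UTI AE needs a positive culture and leukocyturia on a sample with a collection date, and nonserious AESIs are due on the eCRF within 72 hours of site knowledge. UTIs are among the events least likely to lack a day.
- *AE durations are wrong.* SAP 4.3.4 gives a formula, but the output list has no AE-duration summary.
- *The share is 42% (35 days) to 75% (14 days).* That is the chance that a uniform pre-dose onset shares the dosing month, the mean of k/L. It includes AEs still ongoing at dosing, for which the default is kept. It would describe resolved AEs only if each ended on the day it began.

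**Conclusion.** The concern holds as a gap in the date rule, limited to records with a partial onset in the treatment month, or a year-only onset in the treatment year, whose end date is known to precede dosing. An onset in an earlier month goes to the consent date and stays pre-dose.

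For AEs that began and resolved before dosing and lack an onset day, about 25% to 68% would be mislabelled as TEAEs for intervals of 35 to 14 days. These are shares under uniform dates, not forecasts, and they apply to an unstated and probably small number of partial dates. For OAB drugs the year-only rule is the main route. With a 14-day washout and a 3-day diary, the month rule matters only if both start and stop fall in the treatment month, at least 14 + 3 = 17 days before dosing.

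This is a modest defect in descriptive tables. It merits correction because the recorded data already contradict the imputed value and the repair is simple.

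**What to change.** Add a condition to SAP 4.2.3, ahead of the existing onset rules. If the complete or partial end date shows that the record ended before study treatment, impute the onset no later than the end date (for AEs, not before informed consent). Classify the record as not treatment-emergent if it is an AE, or as prior only if it is a medication. Keep the treatment-date default when the end date is on or after dosing, ongoing or unknown.

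The cost is one sentence in the SAP and one condition in the date-imputation program. No new data are needed.
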